Title	Comparison of the ToFscan and TetraGraph during Recovery of Neuromuscular Function in the Post Anesthesia Care Unit
Running Title	ToFscan vs TetraGraph
Phase	N/A
Methodology	Randomized, Open-Label
Overall Study Duration	6 months
Subject Participation Duration	Less than 1 hour
Single or Multi-Site	Multicenter International
Objectives	The primary aim of this study is to assess the agreement and repeatability between TOF values obtained from ToFscan and TetraGraph
Number of Subjects	120 (40 per site)
Diagnosis and Main Inclusion Criteria	Patients undergoing an elective surgery and requiring administration of NMBA intraoperatively
Study Device	TetraGraph
Duration of Administration	Single stimulation of ulnar nerve repeated at specific intervals as outlined in the Study Procedures (Section 6.2)
Reference therapy	ToFscan
Statistical Methodology	This pilot study is meant to be descriptive and it aims to collect basic data for future larger study

4 Introduction

This document is a protocol for a human research study. This study will be carried out in accordance with the applicable United States government regulations and Mayo Clinic research policies and procedures.

4.1 Abstract

Residual neuromuscular blockade is a common occurrence in the post-anesthesia care unit (PACU) when neuromuscular blocking agents (NMBAs) have been used in the operating room. The only method of reliably detecting residual neuromuscular blockade is through the use of quantitative neuromuscular monitors. Unfortunately, several barriers exist that have prevented the widespread application of these devices. For instance, there is a paucity of quantitative neuromuscular monitors commercially available. Also, two modalities of quantitative monitoring, kinemyography and acceleromyography, rely on movement of the muscles of interest, a characteristic frequently compromised during patient positioning for surgical procedures or in uncooperative awake patients in the PACU. Additionally, many clinicians are unfamiliar with these quantitative monitors, and incorporating them into their practice can represent an undesirable educational burden. The aim of this investigation is to compare the performance of two quantitative monitors utilized on post-anesthesia recovering patients. The ToFscan (Draeger Medical Inc., Telford, PA) represents one of the few standalone acceleromyography (AMG)-based quantitative monitors available for routine clinical use in the United States. The TetraGraph (Senzime AB, Uppsala, Sweden) is a standalone electromyography (EMG)-based quantitative monitor that recently received Conformité Européene (CE) approval. While both of these quantitative monitors can be utilized to guide intraoperative NMBA re-dosing and confirm recovery, they provide their objective data via drastically different techniques. AMG, based on Newton's Second law which describes force being proportional to acceleration, measures acceleration of the thumb and requires its unobstructed movement. As such, performing AMG in awake, uncooperative patients can yield inaccurate results because of unwanted patient movement. Alternatively, EMG measures electrical activity within the muscle following peripheral nerve stimulation, and is unaffected by involuntary patient motion. We plan to compare measurements with these two devices throughout various stages of neuromuscular recovery in the PACU and compare the usefulness of these devices in this vulnerable patient population.

4.2 Background

Postoperative residual weakness from neuromuscular blockade continues to be a common problem in the post-anesthesia care unit (PACU). Despite the routine use of reversal agents, a significant number of patients continue to arrive in the PACU with objective evidence of residual neuromuscular blockade (Naguib, Kopman, and Ensor 2007; Cammu et al. 2006). While not every patient with residual weakness develops a postoperative complication, many can develop

avoidable critical respiratory events (Murphy et al. 2008; Berg et al. 1997). Furthermore, special populations such as the elderly, are at particular risk for developing complications related to postoperative residual weakness (Murphy et al. 2015). The use of quantitative monitoring has been demonstrated to reliably reduce the incidence of postoperative residual weakness and the ensuing complications (Todd, Hindman, and King 2014; Todd and Hindman 2015; Murphy et al. 2011). With an abundance of literature supporting the use of objective neuromuscular monitors, a panel of experts recently recommended the universal adoption of such devices whenever NMBA are utilized (Naguib et al. 2018).

Quantitative neuromuscular monitoring devices objectively measure residual weakness and display the results numerically. This is traditionally accomplished by performing a train-of-four (TOF) stimulation at the ulnar nerve and measuring the response of the adductor pollicis muscle. The degree of muscle weakness is determined by calculating the TOF ratio, which consists of the ratio of the fourth muscle contraction to the first. Adequate recovery that excludes clinically significant weakness from neuromuscular blockade is defined as a TOF ratio ≥ 0.9 , a measurement that can be determined reliably only with a quantitative monitor (Sundman et al. 2000; Eriksson et al. 1997). Although evidence strongly suggests objective monitors should be used perioperatively whenever NMBA are administered, these devices can be expensive and require additional training. Many clinicians default to the antiquated practice of utilizing qualitative (subjective) neuromuscular stimulating units such as a peripheral nerve stimulator (PNS) (Grayling and Sweeney 2007; Naguib et al. 2010).

There are several types of quantitative neuromuscular monitors. These devices can be incorporated into the anesthesia workstation, allowing data to be seamlessly integrated into the electronic medical record. Unfortunately, this setup can preclude using these monitors in the PACU as portability is sacrificed. In contrast, other monitors exist as standalone, portable (hand-held) units.

Aside from portability, objective monitors can further be categorized based on the modality utilized to measure responses. Mechanomyography (MMG) measures the force of contraction of the adductor pollicis (thumb) muscle following ulnar nerve stimulation and has served as the traditional “gold-standard”. Mechanomyographic responses are precise and reproducible, however the setup is cumbersome and the lack of commercially available devices has relegated MMG to strictly research purposes. Acceleromyography (AMG) measures acceleration of a muscle group (typically the thumb) in response to stimulation (typically the ulnar nerve). This technique is similar to MMG, but instead of measuring the force of muscle contraction, an accelerometer fixed to the thumb measures the acceleration of the thumb in response to ulnar nerve stimulation. Based on Newton’s Second law that states force is proportional to acceleration, the measured acceleration is correlated with the force of contraction in the clinical setting. There are currently two standalone AMG-based monitors available for clinical use: the STIMPOD (Xavant Technologies, Pretoria, South Africa) and the ToFscan (Draeger Medical Inc., Telford, PA). These devices represent improvements in AMG technology over its predecessor, the TOF-Watch (Schering-Plough Corp., Kenilworth, NJ, USA) as they utilize three

dimensional transducers that can better quantify the complex motion of the thumb. Despite these advances, the use of AMG can be limited due to patient positioning that precludes free motion of the thumb, as well instances of awakening patients moving their thumb during measurements. Kinemyography (KMG) is based on similar principles to AMG, and relies on the thumb being able to move freely. Upon neurostimulation, KMG utilizes a piezoelectric motion sensor that is bent between the thumb and index fingers following muscle contraction. The degree of this bending is quantified and used to determine a TOF ratio. While Datex-Ohmeda (Helsinki, Finland) manufactures a KMG device that can be incorporated into the anesthesia work station, there are no currently available standalone KMG devices. Electromyography (EMG) devices measure electrical activity, termed compound muscle action potentials (cMAPs) following nerve stimulation (typically at the adductor pollicis muscle after ulnar nerve stimulation). As EMG measures cMAPs and does not require freely moving thumbs for accurate measurements, many experts have referred to this monitoring modality as the “new gold standard”. TetraGraph (Senzime AB, Uppsala, Sweden) is a standalone EMG-based device that recently received *Conformité Européene* (CE) approval. We have previously investigated this device and presented our findings at several annual meetings such as International Anesthesia Research Society (May 2018, May 2017, May 2013), the Society for Technology in Anesthesia (January 2018), and the American Society of Anesthesiologists (Octotober 2017, October 2012), European Society of Anaesthesiology (June 2018, June 2015). Furthermore, we have recently submitted abstracts to the PostGraduate Assembly in Anesthesiology in December 2018 as well as a manuscript describing a multi-center, volunteer study investigating TetraGraph versus AMG-based monitors. Our work thus far has found this device to be easy to apply, reliable, and able to provide comparable measurements to other quantitative monitors.

Utilizing recommendations from the Good Clinical Practice (GCP) Guidelines for monitoring of neuromuscular function (Fuchs-Buder et al. 2007), we will investigate the performance of the TetraGraph in patients recovering from anesthesia in the PACU. The postoperative setting is particularly important, as several previous studies performed in awakening patients have reported discordant TOF ratios: accelerographic TOF ratios were not an accurate representation of the neuromuscular status (recovery) of the patients (Baillard et al. 2004). We plan to compare two portable quantitative monitors, the EMG-based TetraGraph and the AMG-based ToFscan. ToFscan has recently been described as an acceptable surrogate for research purposes to the frequently used TOF-Watch (Murphy et al. 2018). The TOF-Watch monitor, however, is no longer manufactured, while the ToFscan is commercially available and approved by the United States Food and Drug Administration (FDA). While the ToFscan has a three-dimensional sensor that can measure acceleration in multiple planes, it still has the same limitations associated with muscle movement inherent to AMG-based quantitative monitors. This is of particular importance in the recovery room when patients may not be fully cooperative when quantitative monitoring is warranted to exclude postoperative residual weakness as a cause of patient distress.

4.3 Risks and Benefits

- The benefits of using neuromuscular blockade monitoring devices:
Early detection of residual neuromuscular blockade
- The risks of using neuromuscular blockade monitoring devices:
Slight discomfort when electrical stimulation is administered

5 Study Objectives

Primary Objective

To assess the agreement and repeatability between TOF values obtained from the ToFscan and TetraGraph during recovery from neuromuscular blockade as measured upon arrival to the PACU, and then 5 (+5 min) and 10 (+10 min) minutes later.

Secondary Objective

Determine the incidence of postoperative residual weakness in the PACU (defined as TOFR <0.90).

Assess patient discomfort associated with each neurostimulation utilizing a verbal numeric rating scale (VNRS) from 0-10.

6 Study Design

6.1 General Description

[figure not shown]
This unblinded, multicenter international, prospective, randomized, observational study will involve 120 patients undergoing surgical procedure that involved administration of neuromuscular blockade agents intraoperatively.

6.2 Number of Subjects

One hundred twenty (forty per site).

6.3 Duration of Participation

10 minutes in PACU

6.4 Primary Study Endpoints

The primary endpoint of the study will be the repeatability of values obtained by ToFscan and TetraGraph monitors.

6.5 Secondary Study Endpoints

The secondary endpoints of the study are the patient outcomes in the postoperative period and discomfort associated with the use of the devices.

6.6 Identification of Source Data

The study data points will be recorded on the developed Case Report Forms (CRFs) by the study team members. In addition to the data collected in the PACU based on the ToFscan and TetraGraph devices ([Table 15.3](#)), several intraoperative characteristics will also be extracted from the medical record ([Table 15.2](#)). These will include type and total dose of NMBA used, time and dose of last NMBA administration, time and dose of specific reversal agent administration, time of tracheal extubation, and TOF ratio at the time of extubation (if available).

7 Subject Selection Enrollment and Withdrawal

7.1 Inclusion Criteria

- Age > or = 18 years old
- Patients willing to participate and provide an informed consent
- Patients undergoing an elective surgical procedure that requires use of non-depolarizing NMBA agents administered intraoperatively.

7.2 Exclusion Criteria

- Patients with unilateral disorders, such as stroke, carpal tunnel syndrome, broken wrist with nerve damage, Dupuytren contracture, or any similar wrist injury.
- Patients with systemic neuromuscular diseases such as myasthenia gravis
- Patients with significant organ dysfunction that can significantly affect pharmacokinetics of neuromuscular blocking and reversal agents, i.e., severe renal impairment or end-stage liver disease.

7.3 Subject Recruitment, Enrollment and Screening

Subjects will be enrolled from the Departments of Anesthesiology at the Mayo Clinic in Florida, NorthShore University Health System, and University of Debrecen. The study has an accrual target of 120 patients. On a daily basis, there are over 20 elective surgical cases performed at Mayo Clinic in Florida and thus no difficulties in accrual based on historical volumes are anticipated. Each participating center reviewed the feasibility and determined that approximately 3 participants per week will be completed for this study. The initial accrual period will last at least 3 months. Patients will be provided with a Research Participant Consent and Privacy Authorization Form describing the study devices, protocol, inclusion and exclusion criteria, as well as risks and benefits of participation.

7.4 Early Withdrawal of Subjects

7.4.1 When and How to Withdraw Subjects

Patients are free to withdraw at any time and for whatever reason. If patient withdraws consent prior to arrival to PACU, the study data will not be collected. If patient withdraws consent after study data was already completed, the participant will need to provide instructions to the study team to remove his/her data from the data set. Pre-specified reasons for discontinuing include, but are not limited to, the following:

- Patient Request: Patient decided that he/she did not want to continue (for any reason)
- Adverse Event: Patient experienced a related or unrelated event that would interfere with the study objectives/evaluation

- Inclusion/Exclusion Discrepancy/Violation: Patient should not have been enrolled
- Other: Any other reason

7.4.2 Data Collection and Follow-up for Withdrawn Subjects

If a Participant withdraws from the study, no additional attempts will be made to contact the Participant.

8 Study Device

8.1 Description

ToFscan is a nerve stimulator module used for the measurement of neuromuscular transmission via accelerometry. ToFscan was developed by Drager Technologies, Canada, and it uses a three-dimensional piezoelectric sensor that attaches to the thumb via a hand adapter to measure acceleration in multiple planes (Murphy et al, 2018).

TetraGraph device is a neuromuscular transmission monitor capable of estimating the depth of neuromuscular block in anesthetized patients who received neuromuscular blocking agents.

TetraGraph uses EMG to measure the muscle action potentials that are generated in response to percutaneous electrical neurostimulation.

8.2 Method for Assigning Subjects to Treatment Groups

This is an open-label pilot investigation and all study participants are assigned to both standard of care and investigational device use in PACU. The randomization involves the use of dominant vs non-dominant arm.

The randomization will be performed utilizing REDCap and assigned anesthesia clinical care team will be informed of patients' assigned to guide them with the selection of the assigned treatment option.

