9.2 Visit 2 (Randomization and Treatment – day of surgery)

- Elective surgical procedure as per standard of care
- Intraoperative neuromuscular blockade, management, and neuromuscular antagonism will be at the discretion of the attending anesthesiologist.
- Upon arrival to the PACU, consenting patients will be randomized to have the TetraGraph placed on either their dominant or non-dominant arm. TetraGraph uses proprietary, single-use surface electrodes (TetraSens™, Senzime AB, Uppsala, Sweden) with stimulating electrodes placed over the ulnar nerve, a reference electrode placed on the adductor pollicis (1st digit) ([Figure 16.1](#)). The skin will be prepped with careful abrasion and cleansing of the skin in the usual fashion prior to electrode placement.
- ToFscan will be placed on the patient's opposite arm. Stimulating electrodes (Red Dot ECG electrodes, 3M, St. Paul, MN) will be placed over the ulnar nerve with the negative electrode near the wrist crease and positive electrode placed 3-4 cm proximally. The skin will be prepped with careful abrasion and cleansing of the skin in the usual fashion prior to electrode placement. The ToFscan utilizes a thumb splint with the encased transducer secured to the hand ([Figure 16.2](#)).
- To obtain measurements with TetraGraph, TOF stimulation will be performed at 50mA and the measurement recorded. This measurement will be repeated twice, 20 seconds apart. If the two measurements differ by >10%, a third measurement will be recorded, with the closest two readings kept and the outlier discarded. If TetraGraph yields a train-of-four count but not a ratio with any measurement, this will be recorded.
- To obtain ToFscan measurements, TOF stimulation will be performed and the measurement recorded. According to the manufacturer, the ToFscan does not require calibration, and the default stimulating current is 50 mA. The TOF measurement will be repeated twice, 20 seconds apart. If the measurements differ by >10%, a third measurement will be repeated, with the closest two readings kept and the outlier discarded. If TetraGraph yields a train-of-four count but not a ratio with any measurement, this will be recorded.

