- Each neurostimulation with the TetraGraph and ToFscan will be conducted simultaneously with two observers. Patients will be queried as to the level of discomfort associated with obtaining measurements ([Figure 16.3](#)). We have previously utilized this scoring system for a large, multi-center volunteer trial (manuscript submitted). If patients are unable to quantify their discomfort, this will be documented.
- The above described process will be repeated for both monitors upon arrival to PACU and after 5 minutes and 10 minutes into the PACU stay.

- ToFscan is an FDA approved monitor, while TetraGraph is CE marked, but not FDA approved yet. If TOF ratios below 0.9 are obtained with the ToFscan at any point during this study, the attending anesthesiologist will be notified, as per usual clinical routine. Possible actions include continued monitoring and supportive care, additional reversal agent administration, or, in extreme cases of weakness, ventilatory support with bilevel positive airway pressure (BiPAP) or tracheal re-intubation.
- Following measurements obtained with both devices at these specified time intervals and assuming TOF ratio is >0.9 , the devices will be removed and the patient will proceed along the standard recovery pathway.
- If at any point the patient describes the discomfort associated with neurostimulation as a verbal numeric score of 7 or higher, the patient will be given the option to discontinue the study.
- Prior to discharge from PACU, patients will be asked to recall if they had a neurostimulation. If they do recall it, we will again query the level of discomfort associated with obtaining measurements ([Figure 16.3](#)).

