10.1 Sample Size Determination

Based on paired t-test, 23 enrolled patients will give 90% power to detect a difference in TOF ratios with a significance level of 0.05 (JMP Pro Software version 13.0.0 [August 23, 2018]; SAS Institute Inc., Cary, NC). We utilized a standard deviation of 0.07 that was determined during our multi-center volunteer study comparing another AMG device and TetraGraph. However, we will enroll 40 patients at 3 sites for a total of 120 patients to account for dropout during the study and to provide further insight into the incidence of postoperative residual weakness and three large centers. The other centers that might be submitting similar studies and

sharing de-identified data for the purposes of data analysis and publication are as follows:

NorthShore University HealthSystem, Evanston, IL, USA [REDACTED]

[REDACTED] and University of Debrecen, Debrecen,

Hungary [REDACTED]. Each

site will complete separate applications for their IRB or Ethics committee approval; Mayo Clinic in Florida will serve as the lead site and will provide oversight to ensure compliance with the protocol at each site. .

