10.2 Statistical Methods

Descriptive Statistics

Analysis of agreement between the devices will be assessed using the method described by Bland and Altman (Olofson et al. 2015). The bias is defined as the mean difference of repeated measurements from the ToFscan and the TetraGraph obtained at the same time intervals. The limits of agreement are defined as $\text{bias} \pm 2 \text{ SD}$, where SD denotes the standard deviations of the differences. Limits of agreement are interpreted as the reference range within which 95% of the differences will lie. The bias and the limits of agreements surrounding the bias ($\pm 2 \text{ SD}$) will be calculated with 95% confidence intervals. Repeatability between the two devices at the various time intervals will also be assessed with significance defined as a p-value <0.05 .

Handling of Missing Data

This is a prospective study and therefore we do not anticipate any missing data. In the event of any unexpected missing data, no attempt to impute this missing data will be made; missing data will simply be treated as missing in the statistical analysis.

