18.3 PACU data

Study ID	
Date of Surgery (dd / mm / yyyy):	

Initials:		Dominant side:	L / R	Age (yrs):	
Weight (kg):		Height (cm):		BMI:	

TetraGraph (TG)

Arm tested: dominant / non-dominant

	TOFR #1	TOFR #2	TOFR #3 (if needed)	VNRS
T0 (on arrival to PACU)				
T5 (5 min later)				
T10 (10 min later)				
Predischarge VNRS	xxx	xxx	xxx	

ToFscan (TS)

Arm tested: -dominant / non-dominant

	TOFR #1	TOFR #2	TOFR #3 (if needed)	VNRS
T0 (on arrival to PACU)				
T5 (5 min later)				
T10 (10 min later)				
Predischarge VNRS	xxx	xxx	xxx	

TG= TetraGraph; TS= ToFscan; TOFR= train-of-four ratio; VNRS= verbal numeric rating scale

19 List of In-Text Figures

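### The agreement analysis does not use the randomised arm, so an average dominant/non-dominant difference would widen the limits of agreement

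*Combined protocol and SAP*

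**What the plan says.** Section 8.2 gives every patient both devices and states what is randomised: "The randomization involves the use of dominant vs non-dominant arm". Section 9.2 sets this out: "consenting patients will be randomized to have the TetraGraph placed on either their dominant or non-dominant arm", and "ToFscan will be placed on the patient's opposite arm". The measurements are then repeated on the same set-up: "The above described process will be repeated for both monitors upon arrival to PACU", and again at 5 and 10 minutes. No exchange of arms is described. The data form in section 18.3 has one entry per device, "Arm tested: dominant / non-dominant", which covers T0, T5 and T10.

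Section 10.2 plans a Bland-Altman analysis: "The bias is defined as the mean difference of repeated measurements from the ToFscan and the TetraGraph obtained at the same time intervals". The limits are the bias ± 2 SD, "where SD denotes the standard deviations of the differences". Neither section 10.2 nor section 10.3 mentions arm, dominance or the allocation, whether as a model term, a stratum or a sensitivity analysis. Section 10.2 cites a methods paper on advanced Bland-Altman analysis, but its own text has no allocation term.

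**The concern.** The plan randomises a factor, records it and then leaves it out of the analysis. Within a patient, the ToFscan-minus-TetraGraph difference is also a difference between arms. If the dominant arm reads on average d higher than the non-dominant arm, the difference is shifted by +d when the TetraGraph is on the non-dominant arm and by −d when it is on the dominant arm. Across a balanced sample these shifts cancel in the mean, but they do not cancel in the SD.

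Agreement between the devices is part of the primary objective in section 5, and the limits are a main output of a Bland-Altman analysis. Limits from pooled raw differences would describe the devices plus an average arm effect, yet would be reported as device disagreement. The synopsis says that the study is to supply basic data for a larger one, so an SD inflated in this way could carry into that study's planning.

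**Working it through.** **Inputs**
- Planning SD: 0.07, from section 10.1: "We utilized a standard deviation of 0.07 that was determined during our multi-center volunteer study comparing another AMG device and TetraGraph". It is taken here as the SD of one ToFscan-minus-TetraGraph difference within an allocation group. That is an assumption.
- Limits: bias ± 2 SD (section 10.2).
- N = 120 (section 6.2); a 60:60 split by allocation is assumed.
- d, the average dominant-minus-non-dominant difference in TOF ratio: not in the documents, so a range is shown.

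**The plan's own figure.** Section 10.1 states 23 patients for 90% power at a significance level of 0.05, but no difference to be detected. A two-sided paired t-test with SD 0.07 and an assumed difference of 0.05 returns 23 (power 90.5%). The difference implied at exactly 90% power is 0.0495. This serves only as a yardstick for d.

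**Model.** For one difference per patient, D = bias + s·d + e, where s = +1 if the TetraGraph is on the non-dominant arm and −1 if it is on the dominant arm, and SD(e) = 0.07. With equal groups:
- mean of D = bias, because the +d and −d terms cancel
- Var(D) = 0.07² + d²
- half-width of the limits = 2 × √(0.07² + d²)

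| d | SD with allocation ignored | Limits | Widening |
|---|---|---|---|
| 0 | √0.0049 = 0.0700 | ±0.140 | – |
| 0.01 | √0.0050 = 0.0707 | ±0.141 | 1% |
| 0.02 | √0.0053 = 0.0728 | ±0.146 | 4% |
| 0.03 | √0.0058 = 0.0762 | ±0.152 | 9% |
| 0.05 | √0.0074 = 0.0860 | ±0.172 | 23% |

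**Check by simulation** (20,000 trials of 120 patients, split 60:60). With allocation ignored, the mean half-width was 0.145 at d = 0.02 and 0.172 at d = 0.05. With the SD pooled within allocation groups it was 0.140 in both cases. The mean bias stayed at about 0 throughout.

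**Precision of the arm effect.** Half the difference between the two group means estimates d. Its standard error is ½ × 0.07 × √(1/60 + 1/60) = 0.0064, so d = 0.02 would lie about 3 standard errors from zero (0.02/0.0064 = 3.1).

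**If 0.07 already contains the arm effect.** The SD after adjustment would be √(0.07² − d²), and the adjusted limits would be ±0.134, ±0.126 and ±0.098 at d = 0.02, 0.03 and 0.05, against ±0.140 unadjusted.

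**What the term cannot remove.** Side-to-side variation that differs between patients, with SD τ, also adds τ² to the variance. At τ = 0.05 the half-width is again 2 × √(0.07² + 0.05²) = 0.172, and an allocation term leaves it unchanged.

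**The case against.** The strongest objection is that nothing in the documents shows a systematic dominance effect or gives its size. The 23% figure needs d = 0.05, an arm effect about as large as the device difference implied by the sample-size calculation (0.0495). At d = 0.02 or below the widening is at most 4%. This stands: the size is conditional and may be negligible.

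Second, section 10.2 already puts 95% confidence intervals on the limits. With SD 0.07 and one difference from each of 120 patients, the half-width of that interval is about 1.96 × 0.07 × √(1/120 + 4/238) = 0.022. The widening is 0.006 at d = 0.02 and 0.012 at d = 0.03, both smaller; only d = 0.05 (0.032) exceeds it. The comparison is fair, but sampling error shrinks with more patients and this widening does not. The interval would also be centred on the wider limit.

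Third, the 0.07 may already include arm variation, because section 10.1 does not say how the volunteer study placed its devices. This stands as a caveat on the baseline. It does not change the direction of the effect.

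Fourth, section 7.2 excludes unilateral disorders and wrist injuries. That limits gross side differences, but not an ordinary dominance effect.

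Fifth, the study is a descriptive pilot, section 10.2 sets no acceptable limit of agreement, and limits that are too wide understate agreement. The arm is recorded, so the adjustment could be made later. All of this lowers the urgency. It is still better to specify the term now than to choose between adjusted and unadjusted limits after seeing both.

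**Conclusion.** The point holds as a gap in the analysis that can be closed at almost no cost. Section 10.2 ignores a randomised and recorded factor, and an average arm effect d would raise the SD of the differences to √(0.07² + d²). With 0.07 as the within-allocation SD and equal groups, the limits widen by 4%, 9% and 23% at d = 0.02, 0.03 and 0.05. The documents do not say where in that range, or below it, the truth lies.

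A reader might infer three stronger things that the documents do not support:
- **That the bias is confounded with arm.** Device and arm are tied within a patient, but randomising the arm breaks the link across patients, so the expected bias is protected. Chance imbalance leaves little: an illustrative 65:55 split with d = 0.05 moves the bias by 0.05 × 10/120 = 0.004, below its standard error of 0.07/√120 = 0.0064. Section 8.2 does not mention blocking, but that silence does not show that the allocation is unblocked.
- **That every arm difference can be adjusted away.** An allocation term removes only the average effect.
- **That the devices should swap arms.** Section 9.2 has both devices stimulate simultaneously, which opposite arms make possible. The analysis change does not depend on a swap.

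**What to change.** In section 10.2, specify a repeated-measures Bland-Altman model for the ToFscan-minus-TetraGraph differences, with the randomised allocation (TetraGraph on the dominant or the non-dominant arm) as a fixed term and patient as a random effect across T0, T5 and T10. Then report:
- the bias as the simple average of the two allocation-group means
- half the difference between those means, with its 95% confidence interval, as the arm effect
- the limits from the total SD, √(between-patient variance + within-patient variance), after removing the allocation effect
- the unadjusted limits alongside

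Add a sentence saying that patient-specific arm-to-arm variation stays mixed with device disagreement because the devices are always on opposite arms, so the conclusions apply to the two devices used in that way.

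The cost is a few sentences in section 10.2 and one degree of freedom. It needs no new patients, data or procedures, since section 18.3 already records the arm. If d proves close to zero, the adjusted and unadjusted limits will nearly coincide and almost nothing is lost.
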